4.6 Risks and benefits

The risk to subjects in this trial may be minimized by compliance with the eligibility criteria and study procedures, as well as close clinical monitoring. Further, dose modifications are provided and must be applied per protocol based on clinical or laboratory findings (see [Section 6.5.3](#)).

Occurrence of an immune-related adverse event is an anticipated risk in subjects treated with immune-oncology drugs such as MBG453. In the case of an immune-related event, there are dose modification and management guidelines, including detailed plans for follow-up of toxicities. In addition, the protocol references and will adhere to recent American Society of Clinical Oncology (ASCO) practices guidelines for management of immune-related adverse events in patients treated with checkpoint inhibitors ([Schneider et al 2021](#)) (see [Section 6.5.3](#) and [Section 6.5.4.1](#)).

Based on currently available data, there are no known significant overlapping toxicities between the combination of venetoclax and azacitidine and MBG453. However, this novel combination treatment may have unforeseen risks, which could be serious. In particular, there is the potential for increased toxicity secondary to cytokine release syndrome due to activation of T cells and macrophages, and there may also be changes in immune function that could lead to autoimmunity or other immune-related adverse events as well as increased risk of infection. All subjects enrolled will be monitored closely for these potential toxicities.

Furthermore, as the safety of MBG453 administered in combination with azacitidine + venetoclax has not been assessed previously, the protocol stipulates that consecutive safety run-

in cohorts at 400 mg Q4W and 800 mg Q4W will be observed for at least 2 treatment cycles followed by a Safety Review Meeting, before opening enrollment to a larger patient population in Part 2. See [Section 6.5.1](#). In addition, a Steering Committee (see [Section 10.2.2](#)) will review the safety during the course of the study.

Women of child bearing potential and sexually active males must be informed that taking the study treatment may involve unknown risks to the fetus if a pregnancy were to occur during the study and must agree that in order to participate in the study they must adhere to the contraception requirements outlined in the exclusion criteria until at least 30 days after the last dose of venetoclax, 90 days after the last dose of azacitidine (or as per respective local labels, whichever is longer) and 150 days after the last dose of MBG453, whichever is later. If there is any question that the subject will not reliably comply, they should not be entered or continue in the study.

No substantial additional risk to patients' safety due to the SARS-CoV-2 virus and the COVID-19 pandemic has been identified with MBG453 based on the available knowledge at this time. In case of active COVID-19 infection, a careful benefit risk evaluation needs to be performed by the investigator to determine whether the subject should remain on study medication or not.

There is no contraindication for the use of an inactivated, viral-vector-, or mRNA based SARS-CoV-2 vaccine in cancer patients on sabatolimab therapy.

COVID-19 vaccines have not been tested in patients treated with MBG453, therefore any additional risks are unknown at this time. Before receiving any vaccine, the risks and benefits should be evaluated by the investigator.

4.7 Rationale for Public Health Emergency mitigation procedures

In the event of a Public Health emergency as declared by Local or Regional authorities (i.e. pandemic, epidemic or natural disaster), mitigation procedures may be required to ensure participant safety and trial integrity and are listed in relevant sections of the study protocol. Notification of the Public health emergency should be discussed with Novartis prior to implementation of mitigation procedures and permitted/approved by Local or Regional Health Authorities and Ethics Committees as appropriate.

5 Population

The study population will include adult subjects with newly diagnosed AML, who are not suitable for intensive chemotherapy and not eligible for HSCT. Approximately 18 subjects across two dose levels, are expected to be enrolled in the safety run-in; additional subjects will be enrolled in the expansion part to achieve total enrollment of approximately 86 subjects.

Subjects with secondary AML, including therapy-related AML, may be included provided Inclusion criterion #3 is met and Exclusion criterion #4 is not met.

The investigator or designee must ensure that only subjects who meet all the following inclusion and none of the exclusion criteria are offered treatment in the study.

5.1 Inclusion criteria

Subjects eligible for inclusion in this study must meet **all** of the following criteria:

1. Signed informed consent must be obtained prior to participation in the study
2. Age \geq 18 years at the date of signing the informed consent form (ICF)
3. Newly diagnosed with AML (based on WHO 2016 classification ([Arber et al 2016](#)), who are not suitable for intensive chemotherapy based on one or more of the following criteria:
 - age \geq 75 years
 - ECOG performance status of 2 or 3
 - or at least one of the following comorbidities:
 - severe cardiac comorbidity (including congestive heart failure requiring treatment, ejection \leq 50%, or chronic stable angina)
 - pulmonary comorbidity (including DLCO \leq 65% or FEV1 \leq 65%)
 - moderate hepatic impairment with total bilirubin $>$ 1.5 to 3 times the upper limit of normal
 - eGFR \geq 30 mL/min/1.73 m² to $<$ 45 mL/min/1.73 m² (estimation based on Modification of Diet in Renal Disease (MDRD) formula, by local laboratory)
 - any other comorbidity (to be documented in the CRF) that the physician judges to be incompatible with intensive chemotherapy must be reviewed and approved by the Novartis Medical Monitor before study enrollment.

Patients with antecedent MDS, myelofibrosis, essential thrombocythemia, or polycythemia vera may be included, provided no prior therapy, as specified in exclusion criterion # 1.

4. No planned hematopoietic stem-cell transplantation (HSCT).
5. Eastern Cooperative Oncology Group (ECOG) performance status of 0, 1, 2, or 3
6. AST and ALT \leq 3 \times upper limit of normal (ULN)
7. Total bilirubin \leq 3.0 \times ULN (except in the setting of isolated Gilbert syndrome, in which case higher total bilirubin is allowed provided that conjugated bilirubin is \leq 3.0 x ULN)
8. Estimated Glomerular Filtration Rate (eGFR) \geq 30 mL/min/1.73 m² (estimation based on Modification of Diet in Renal Disease (MDRD) formula, by local laboratory)
9. Subject is able to communicate with the investigator, and has the ability to comply with the requirements of the study procedures
10. WBC $<$ 25x10⁹/L (may be reduced with leukapheresis or hydroxyurea)

5.2 Exclusion criteria

Subjects meeting **any** of the following criteria are **not** eligible for inclusion in this study

1. Previous treatment at any time, with any of the following antineoplastic agents, approved or investigational; checkpoint inhibitors, venetoclax and hypomethylating agents (HMAs) such as decitabine or azacitidine. Previous treatment for AML, MDS, myelofibrosis, essential thrombocythemia, or polycythemia vera, with the exception of hydroxyurea, growth factors, and supportive care ruxolitinib
2. Prior exposure to TIM-3 directed therapy at any time.

4. Subjects with AML-M3 / APL (Acute promyelocytic leukemia) with PML-RARA and patients with AML secondary to Down's syndrome
5. Subjects with CNS leukemia or neurologic symptoms suggestive of CNS leukemia (unless CNS leukemia has been excluded by a lumbar puncture)
6. Subjects with concurrent or prior malignancy, **except:**
 - a) subject with history of MDS, myelofibrosis, essential thrombocythemia, or polycythemia vera
 - b) subject with history of adequately treated malignancy for which the subject has been disease free (absence of residual disease) for at least 1 year and if no anticancer systemic therapy (namely chemotherapy, radiotherapy or surgery) is ongoing or required during the course of the study. Patients who are receiving adjuvant therapy such as hormonotherapy are eligible
7. History of severe hypersensitivity reactions to any ingredient of study drug(s) (azacitidine, venetoclax, MBG453) or monoclonal antibodies (mAbs) and/or their excipients
8. Any concurrent severe and/or uncontrolled medical condition e.g., active uncontrolled infection or severe infectious disease requiring parenteral antibacterial, antiviral or antifungal therapy (such as severe pneumonia, meningitis, or septicemia)
9. Active autoimmune disease requiring systemic therapy (e.g. corticosteroids)
11. Subject has consumed grapefruit, grapefruit products, Seville oranges (including marmalade containing Seville oranges) or Starfruit within 3 days prior to the initiation of study treatment (C1D1).
12. Current use, or use within 14 days prior to enrollment, of systemic steroid therapy or any immunosuppressive therapy (≥ 10 mg/day prednisone or equivalent). Topical, inhaled, nasal and ophthalmic steroids are not prohibited. Replacement therapy is allowed and not considered a form of systemic treatment
13. Live vaccine administered within 30 days prior to the first day of study treatment (C1D1)
14. Cardiac or cardiac repolarization abnormality, including but not limited to any of the following:
 - a) History of myocardial infarction (MI), angina pectoris, or coronary artery bypass graft (CABG) within 6 months prior to starting study treatment
 - b) QTcF > 470 ms at screening (based on mean of triplicate ECG), long QT syndrome or family history of unexplained cardiac death
 - c) Clinically significant cardiac arrhythmias (e.g., ventricular tachycardia), complete left bundle branch block, high-grade AV block (e.g., bifascicular block, Mobitz type II and third degree AV block)
15. HIV infection not controlled by standard therapy (as permitted per protocol [Section 6.2.1.1](#)) and/or with known history of opportunistic infection. For countries where HIV status is mandatory: HIV status will be tested during screening using a local test
16. Active Hepatitis B (HBV) or Hepatitis C (HCV) infection. Subjects whose disease is controlled under antiviral therapy should not be excluded
17. Other co-morbidity that, in the opinion of the investigator, predisposes the subject to high risk of noncompliance with the protocol

18. Sexually active males unless they use a condom during intercourse while taking azacitidine and for 3 months after stopping this drug. They should not father a child in this period. A condom is required to be used also by vasectomized men in order to prevent delivery of the drug via seminal fluid. In addition, male participants must not donate sperm for the time period specified above.
19. Subject is pregnant or breastfeeding
20. Women of child-bearing potential, defined as all women physiologically capable of becoming pregnant, unless they are using highly effective methods of contraception during study treatment and for 30 days after the last dose of venetoclax, 90 days after the last dose of azacitidine (or as per their respective local labels, whichever is longer) and 150 days after the last dose of MBG453. It is currently unknown whether venetoclax may reduce the effectiveness of hormonal contraceptives, and therefore women using hormonal contraceptives should add a barrier method. Highly effective contraception methods include:
 - Total abstinence (when this is in line with the preferred and usual lifestyle of the subject. Periodic abstinence (e.g., calendar, ovulation, symptothermal, post-ovulation methods) and withdrawal are not acceptable methods of contraception
 - Female sterilization (have had surgical bilateral oophorectomy with or without hysterectomy), total hysterectomy or bilateral tubal ligation at least 6 weeks before taking study treatment. In case of oophorectomy alone, only when the reproductive status of the woman has been confirmed by follow up hormone level assessment
 - Male sterilization (at least 6 months prior to screening/baseline). For female subjects on the study the vasectomized male partner should be the sole partner
 - Use of oral (estrogen and progesterone), injected or implanted combined hormonal methods of contraception or placement of an intrauterine device (IUD) or intrauterine system (IUS) or other forms of hormonal contraception that have comparable efficacy (failure rate <1%), for example hormone vaginal ring or transdermal hormone contraception

In case of use of oral contraception women should have been stable on the same pill for a minimum of 3 months before taking study treatment.

Women are considered post-menopausal and not of child-bearing potential if they have had over 12 months of natural (spontaneous) amenorrhea with an appropriate clinical profile (e.g. age appropriate [generally age from 40 to 59 years], history of vasomotor symptoms) in the absence of other medical justification or have had surgical bilateral oophorectomy (with or without hysterectomy) or bilateral tubal ligation at least 6 weeks ago. In the case of oophorectomy alone, only when the reproductive status of the woman has been confirmed by follow up hormone level assessment is she considered not of child-bearing potential.

If local regulations deviate from the contraception methods listed above to prevent pregnancy, local regulations apply and will be described in the ICF.

6 Treatment

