6.1.3 Treatment arms/group

6.1.4 Guidelines for continuation of treatment

Per protocol, dose modifications, including dose interruptions, for toxicities are permitted and are outlined in [Section 6.5](#).

For patients who achieve a CR and have received at least 18 cycles of study treatment, treatment with venetoclax and azacitidine may be discontinued at the discretion of the investigator, and the patient continued on study receiving only single agent MBG453.

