Male participants, including vasectomized men, in the study, must agree not to father a child and to use a condom during intercourse, to prevent delivery of the drug via seminal fluid during the study, and for the period of 3 months after the last dose of azacitidine.

Prior to starting treatment, male subjects are advised to seek consultation on sperm storage and female subjects of child-bearing potential should seek consultation regarding oocyte cryopreservation.

A copy of the approved version of all consent forms must be provided to Novartis/sponsor after IRB/IEC approval.

Subjects will be asked to complete an optional questionnaire to provide feedback on their clinical trial experience (Trial Feedback Questionnaire (TFQ) see [Section 8.5.1.2](#)) per the schedule indicated in [Table 8-1](#).

As per [Section 4.7](#) during a public health emergency as declared by local or regional authorities i.e. pandemic, epidemic or natural disaster, that may challenge the ability to obtain a standard written informed consent due to limits that prevent an on-site visit, Investigator may conduct the informed consent discussion remotely (e.g. telephone, videoconference) if allowable by a local health authority.

Guidance issued by local regulatory bodies on this aspect prevail and must be implemented and appropriately documented (e.g. the presence of an impartial witness, sign/dating separate ICFs by trial participant and person obtaining informed consent, etc.).

8 Visit schedule and assessments

Assessment schedule [Table 8-1](#) lists all of the assessments when they are performed. All data obtained from these assessments must be supported in the subject's source documentation.

Each treatment cycle is 28 days. Screening evaluations should be performed within \leq 28 days of Cycle 1 Day 1 (except for the pregnancy test which has to be performed within 72 hours before the first dose).

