Medical documentation of oophorectomy, hysterectomy, or tubal ligation must be retained as source documents. Subsequent hormone level assessment to confirm the woman is not of child-bearing potential must also be available as source documentation in the following cases:

1. Surgical bilateral oophorectomy without a hysterectomy
2. Reported 12 months of natural (spontaneous) amenorrhea with an appropriate clinical profile.

In the absence of the above medical documentation, FSH testing is required of any female subject regardless of reported reproductive/menopausal status at screening/baseline.

All pre-menopausal women who are not surgically sterile will have pregnancy testing. Additional pregnancy testing might be performed if requested by local requirements.

At screening, a serum pregnancy test (serum β -HCG) must be performed within 3 days before the first dose.

During the study, a urine/serum pregnancy test should be performed at Day 1 of each cycle (except Cycle 1 if a pregnancy test had been performed within 72 hours of the first dose) and a serum pregnancy test at EOT visit. Pregnancy testing (urine/serum) should occur at monthly intervals during the 150-day safety follow-up period. Refer to [Table 8-1](#) for pregnancy testing schedule.

A positive urine pregnancy needs to be confirmed with a serum test. Confirmed positive pregnancy test requires immediate discontinuation of study treatment and discontinuation from study. See [Section 10.1.4](#) for pregnancy reporting.

The pregnancy tests will be recorded only in the source documentation, not in the CRF.

Women of childbearing potential should employ the use of highly effective contraception during study treatment, for 90 days after the last dose of azacitidine, 30 days after the last dose of venetoclax (or as per their respective local labels, whichever is longer) and 150 days after the last dose of MBG453. Highly effective contraception methods are defined in [Section 5.2](#).

A condom is required for all sexually active male participants to prevent them from fathering a child AND to prevent delivery of study treatment via seminal fluid to their partner while taking azacitidine and for 3 months after stopping this drug. In addition, male participants should not donate sperm for the time period specified above.

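### The protocol gives men three inconsistent contraception periods (section 4.6; exclusion 18 with section 8.4.3; section 7), and they need to be reconciled into one.

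*Protocol*

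**What the plan says.** Four places in the current protocol text tell men how long contraception must last.

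- **Section 5.2, criterion 18** excludes "Sexually active males unless they use a condom during intercourse while taking azacitidine and for 3 months after stopping this drug". The bans on fathering a child and donating sperm cover the same period. MBG453 and venetoclax are not mentioned.
- **Section 8.4.3** repeats that clock: "while taking azacitidine and for 3 months after stopping this drug". It also covers sperm donation.
- **Section 7** asks men to agree to use a condom and not father a child "during the study, and for the period of 3 months after the last dose of azacitidine". It does not mention sperm donation.
- **Section 4.6** opens with "Women of child bearing potential and sexually active males must be informed that taking the study treatment may involve unknown risks to the fetus" and says "they must adhere to the contraception requirements outlined in the exclusion criteria until at least 30 days after the last dose of venetoclax". It then adds 90 days after azacitidine (or the respective local labels if longer) "and 150 days after the last dose of MBG453, whichever is later".

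The women's rule, criterion 20, names all three drugs with the same periods as section 4.6. Only the male text disagrees.

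Two provisions allow MBG453 to continue after azacitidine has stopped. Under section 6.1.4, after a CR and at least 18 cycles, azacitidine and venetoclax may be dropped and "the patient continued on study receiving only single agent MBG453". Under section 6.5.3, a patient who cannot tolerate one or two of the drugs may continue on the rest at any time.

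**The concern.** Section 4.6 sends men to the exclusion criteria for their requirements but attaches its own end dates. The male criterion it points to has no MBG453 period. A site reading 4.6, 5.2, 7 and 8.4.3 together cannot tell a man a single date on which his obligation ends.

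This is a reproductive-safety instruction with consequences for participation. Section 4.6 says that anyone whose reliable compliance is in doubt should not enter or stay in the study, so a man who follows criterion 18 exactly could still fall short of 4.6. Section 8.4.3 also gives its purpose as keeping study treatment from reaching the partner. Section 6.1 defines study treatment as all three drugs, yet the clock in 8.4.3 follows only one. Section 10.1.4 does not collect pregnancy outcomes in partners of male participants, so the study would not record a consequence. No efficacy endpoint, estimand or planned analysis is affected.

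**Working it through.** The plan gives no figure to reproduce. The check sets the end dates side by side.

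**Inputs** (section 6.1.1 unless stated)
- Cycles last 28 days, with no delay (assumption).
- The last azacitidine dose is on Day 7, 8 or 9, depending on the schedule.
- MBG453 is given on Day 8. Venetoclax is given daily, with a last dose on Day 28.
- 3 months is taken as 90 to 92 days (assumption).
- No local label pushes the azacitidine period past the MBG453 period (assumption). In step 1 it would have to exceed 158 − 9 = 149 to 158 − 7 = 151 days to do so.

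Day 1 is the first day of the last cycle that contains azacitidine.

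**Step 1: all drugs stop in the same cycle**
- Criterion 18 and 8.4.3 end between 7 + 90 = Day 97 and 9 + 92 = Day 101.
- Under section 4.6, venetoclax gives 28 + 30 = Day 58, azacitidine gives Day 97 to 99, and MBG453 gives 8 + 150 = Day 158. The latest is Day 158.
- Gap: 158 − 101 = 57 to 158 − 97 = 61 days.

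**Step 2: MBG453 continues for k more cycles without azacitidine, against criterion 18 and 8.4.3**
- Section 4.6 ends on Day 158 + 28k. Criterion 18 still ends on Day 97 to 101.
- The third azacitidine-free cycle runs from Day 85 to Day 112, with MBG453 on Day 92 and the next dose on Day 120. Criterion 18 therefore lapses between those two doses, while dosing continues.
- The gap is 57 + 28k to 61 + 28k days. For k = 6 (illustrative) it is 225 to 229 days.

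**Step 3: the same case against section 7**

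On the narrowest reading, study time ends with the last MBG453 dose, Day 8 + 28k. Section 7 then ends on the later of that day and Day 97 to 101.

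| k | Section 4.6 ends | Section 7 ends | Gap (days) |
|---|---|---|---|
| 0 | 158 | 97–101 | 57–61 |
| 1 | 186 | 97–101 | 85–89 |
| 2 | 214 | 97–101 | 113–117 |
| 3 | 242 | 97–101 | 141–145 |
| 4 | 270 | 120 | 150 |
| 5 or more | 158 + 28k | 8 + 28k | 150 |

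The gap never exceeds 150 days and always falls after the last MBG453 dose. If study time includes the safety follow-up of section 9.1.1.1, which runs 150 days from the last MBG453 dose, the gap is zero. If it also includes survival follow-up (section 9.1.1.3), section 7 runs past section 4.6. The protocol does not say which reading is meant.

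**The case against.** The strongest reply is that section 7 already protects the case that looks worst. A man on MBG453 alone remains on study, so section 7 requires condom use and no fathering throughout dosing. A reader might infer from criterion 18 that such a man has no obligation at all, and that the gap grows without limit, to about a year after 12 more cycles (12 × 28 = 336; 336 + 150 − 90 = 396 days). The documents do not support that. The figure compares 4.6 with criterion 18 and 8.4.3 alone, and its 336 days of dosing fall under section 7. This part of the objection stands.

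The second reply is that section 4.6 is the odd one out. For the time after treatment, 5.2, 7 and 8.4.3 all give men 3 months from azacitidine, and 4.6 refers to the exclusion criteria for the requirements. The Amendment 5 log describes the edit to that paragraph as concerning women and consistency with criterion 20. The women's periods may therefore have been placed in a sentence that also names men. That is plausible but is not proof, and the current sentence expressly includes males. A reader might infer that criterion 18 is the faulty text; the documents do not show that either.

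The third reply concerns urgency. All 90 subjects had been enrolled by Amendment 5, and SAP section 1 records early termination, with a letter to investigators on 11-Jan-2024. Whether any men remain on treatment or in the follow-up window is not shown, though protocol sections 9.1.4 and 9.2 provide for continued treatment. Nor do the documents show which section sites counsel from. The consent form is a separate document that is not available here, so its wording is unknown.

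**Conclusion.** The inconsistency is real and lies in current text. Men have three different end points, and a site cannot apply all of them. The difference is about 57 to 61 days between section 4.6 and criterion 18 when all drugs stop in one cycle. When MBG453 outlasts azacitidine, criterion 18 and 8.4.3 lapse during dosing. Measured against section 7, what remains is at most 150 days after MBG453 ends, and less or nothing if follow-up counts as study time. Section 7 does not mention sperm donation, so that rule has no on-study limb outside section 4.6.

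These sizes rest on undelayed 28-day cycles, 3 months read as 90 to 92 days, and no longer local label governing. This is a consistency fault that bears on safety. It is not evidence that any partner was exposed, and it does not show which passage is wrong.

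**What to change.** Reconcile section 4.6, exclusion criterion 18, section 7 and section 8.4.3. The sponsor should choose one male period covering condom use, fathering and sperm donation, state it by drug as criterion 20 does for women, and say explicitly what applies to a man who continues MBG453 after azacitidine stops. If the study-time wording of section 7 is kept, define whether it includes safety and survival follow-up. Align the consent form if it differs, and notify sites that have any men still on treatment or in the follow-up window. No period is proposed here; the choice is the sponsor's.

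The cost is wording in four protocol sections, a consent-form check and a site letter where men remain. No new procedure or data collection is needed.
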